**Safety Analyses**

Adverse events will be summarized by MedDRA system organ class and preferred term. Separate tabulations will be produced for all treatment-emergent adverse events, treatment-related adverse events (those considered by the Investigator as at least possibly drug related), serious adverse events, discontinuations due to adverse events, and adverse events of at least Grade 3 severity. By-patient listings will be provided for deaths, serious adverse events, and events leading to discontinuation of treatment.

Descriptive statistics will be provided for clinical laboratory data and vital signs data, presented as both actual values and changes from baseline relative to each on-study evaluation and to the last evaluation on study.

In addition, shift tables of laboratory data from baseline to worst value on treatment will be presented based on CTCAE v 4.03 grading.

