***PROTOCOL SYNOPSIS:***

Title: A Phase 2b Study of Immune Checkpoint Inhibition With or Without Dorgenmeltucel-L (HyperAcute Melanoma) Immunotherapy for Patients with Stage IV Melanoma

Primary Objectives: *Safety:* To determine the safety of administration of immune checkpoint inhibition with or without dorgenmeltucel-L (HyperAcute Melanoma (HAM)) immunotherapy for patients with Stage IV melanoma.

*Efficacy:* To assess the progression-free survival (PFS) of metastatic melanoma patients treated with immune checkpoint inhibition with or without dorgenmeltucel-L immunotherapy.

Secondary Objective: *Efficacy:* To assess the overall response rate, duration of response, duration of stable disease, and overall survival (OS) of patients with Stage IV melanoma treated with immune checkpoint inhibition with or without dorgenmeltucel-L immunotherapy.

*Biologic activity:* To measure possible anti-tumor immune responses in melanoma metastases in patients. To further determine whether the humoral and cellular mediated arms of the host immune system are activated secondary to dorgenmeltucel-L combined with immune checkpoint inhibition. Lastly, to perform correlative studies of patient blood samples (and tumor when available) to determine the mechanism of any observed anti-tumor effect.

Population: Patients with Stage IV metastatic melanoma  
**Arm 1:** Patients will receive immune checkpoint inhibition plus dorgenmeltucel-L  
Immune checkpoint inhibition consists of the treating physician's standard of care choice of ipilimumab, nivolumab, or pembrolizumab.  
**Arm 2:** Patients will receive immune checkpoint inhibition alone  
Immune checkpoint inhibition consists of treating physician's standard of care choice of ipilimumab, nivolumab, or pembrolizumab.

Sample Size: One hundred total patients will be randomized with equal allocation to Arm 1 (50 patients) and Arm 2 (50 patients). Patients will be stratified by immune checkpoint therapy and disease status and categorized as follows:

- 1) Immune checkpoint inhibition
- 2) Patients with unresectable advanced disease
- 3) Patients with resectable advanced disease who receive the immunotherapy in advance of resection

- 4) Patients with resected isolated advanced disease who are treated in a no apparent disease (NAD) state

Investigational Drugs:

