## 1 INTRODUCTION

### 1.1 Objectives

#### 1.1.1 Primary Objective:

To assess safety of an anti-tumor treatment using immune checkpoint inhibition consisting of ipilimumab, nivolumab, or pembrolizumab alone compared to immune checkpoint inhibition plus dorgenmeltucel-L immunotherapy in Stage IV melanoma patients and to assess efficacy as indicated by progression-free survival of those patients treated with immune checkpoint inhibition with or without dorgenmeltucel-L immunotherapy.

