### **Specific Risk/Adverse Events with ipilimumab**

Ipilimumab can result in severe and fatal immune-mediated adverse reactions due to T-cell activation and proliferation. These immune-mediated reactions may involve any organ system; however, the most common severe immune-mediated adverse reactions are enterocolitis, hepatitis, dermatitis (including toxic epidermal necrolysis), neuropathy, and endocrinopathy. The majority of these immune-mediated reactions initially manifested during treatment; however, a minority occurred weeks to months after discontinuation of ipilimumab.

Permanently discontinue ipilimumab and initiate systemic high-dose corticosteroid therapy for severe immune-mediate reactions. Assess patients for signs and symptoms of enterocolitis, dermatitis, neuropathy, and endocrinopathy and evaluate clinical chemistries including liver function tests and thyroid function tests at baseline and before each dose. For specific details of toxicity management, the treating physician is instructed to refer to the package insert for ipilimumab and to follow the instructions and algorithms therein.

Specific attention to development of autoimmune events during periodic study visits can be evaluated by an optional checklist provided in **Appendix E**. This checklist in addition to the serologic tests obtained can be used by the study physicians to determine if further evaluation for autoimmune disease is warranted by an appropriate specialist in the organ system affected. This can be done to avoid misinterpretation of spurious autoimmune test results.

Trials using immunomodulatory agents such as ipilimumab CTLA-4 have shown a correlation between disease response and so called autoimmune breakthrough events (ABEs) like hypophysitis, colitis, autoimmune hepatitis, or dermatitis. It is for this reason that they are distinguished from other adverse events.

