### **Specific Risks / Adverse Events**

Pembrolizumab can cause severe immune mediated adverse events and can involve multiple organ systems. Severe immune mediated adverse events include pneumonitis, colitis, hepatitis, hypophysitis, nephritis, and hypothyroidism and hyperthyroidism. Additional severe immune mediated adverse events can include dermatitis, uveitis, myositis, pancreatitis, and adrenal insufficiency.

For suspected immune-mediated adverse reactions, ensure adequate evaluation to confirm etiology or exclude other causes. Based on the severity of the adverse reaction, withhold pembrolizumab and administer corticosteroids.

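### Safety is a primary between-arm objective, but the safety tables have no immune-mediated grouping and no between-arm estimate, so a rise spread over several organs would be hard to tell from noise

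*Combined protocol and SAP*

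**What the plan says.** The Protocol Synopsis makes safety a primary objective: "To determine the safety of administration of immune checkpoint inhibition with or without dorgenmeltucel-L". Section 1.1.1 frames it as a comparison, with checkpoint inhibition "alone compared to immune checkpoint inhibition plus dorgenmeltucel-L immunotherapy in Stage IV melanoma patients".

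Section 12.3, Safety Analyses, gives the method: "Adverse events will be summarized by MedDRA system organ class and preferred term". Separate tables follow for all treatment-emergent events, treatment-related events, "serious adverse events, discontinuations due to adverse events, and adverse events of at least Grade 3 severity". There are also by-patient listings, descriptive laboratory and vital-sign summaries, and laboratory shift tables to the worst CTCAE grade. No table groups immune-mediated or autoimmune events, and no between-arm difference or interval is planned for any safety result.

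On the expected harm, Section 5.2 says of ipilimumab: "These immune-mediated reactions may involve any organ system". Section 5.4 says: "Pembrolizumab can cause severe immune mediated adverse events and can involve multiple organ systems". Section 5.3 gives a similar multi-organ list for nivolumab. Section 11.3 names autoimmune disease as a theoretical risk of the immunization itself.

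Section 5.2 also says of autoimmune breakthrough events under agents such as ipilimumab: "It is for this reason that they are distinguished from other adverse events". Section 10.4 directs that events already reported for a checkpoint inhibitor be attributed to that drug.

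**The concern.** The trial adds an immune-activating vaccine to drugs whose main toxicity is immune-mediated. The natural safety question is whether the vaccine raises that toxicity overall. System organ class and preferred term split it into colitis, hepatitis, pneumonitis, thyroid disease, skin reactions and so on. With 50 patients per arm, each term may hold only a few cases.

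The pooled tables do not isolate the question either:

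- The all-event total in Arm 1 will be dominated by injection-site reactions, which Section 5.1 says most recipients have.
- The serious, discontinuation and Grade 3 or higher tables mix immune events with disease-related and other events.
- The related-event table depends on attribution. Under Section 10.4, a vaccine-driven rise in a known checkpoint-inhibitor event may be credited to the checkpoint inhibitor.

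At stake is whether the trial's tables can answer a question it calls primary.

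**Working it through.** **The plan's own figure.** The documents state no safety figure, so I checked only the arm size and alpha that I borrow. Section 12.1 gives 22% v 42%, 80% power, two-sided 0.20 and 100 patients.

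n per arm = [z(0.90)·√(2·p̄·q̄) + z(0.80)·√(p₁q₁ + p₂q₂)]² / d², with p̄ = 0.32 and d = 0.20

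= [1.2816 × √0.4352 + 0.8416 × √0.4152]² / 0.04 = [0.8455 + 0.5423]² / 0.04 = 48.1, so 49 per arm (98 in total, against 100 stated). Power at 50 per arm is 81.1%. The figure reproduces.

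**Inputs for the safety check.** From the documents: 50 per arm and two-sided 0.20. Assumed: 20% v 40% of patients with any immune-mediated event, split evenly over six non-overlapping organ terms (20/6 = 3.3% v 40/6 = 6.7% each). Since Section 12.3 plans no safety test, the 0.20 level only gauges how visible a difference would be.

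**Composite against one given term.** Statistic: z = (p̂₁ − p̂₂) / √(p̄·q̄·2/50), critical value 1.2816, with power by exact binomial enumeration. At the expected counts:

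- Composite: 10 v 20 patients, p̄ = 0.30, z = 0.20 / √0.0084 = 2.18.
- One term: 1.7 v 3.3 patients, p̄ = 0.05, z = 0.0333 / √0.0019 = 0.76.

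| Assumed overall rates | Composite | One given term (of six) |
|---|---|---|
| 20% v 40%, level 0.20 | 83% | 36% |
| 15% v 30%, level 0.20 | 70% | 33% |
| 30% v 50%, level 0.20 | 77% | 32% |
| 20% v 40%, level 0.05 | 60% | 10% |

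The 36% includes about 3 points of rejections in the wrong direction.

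**Scanning all six terms.** A reader sees every term, so the single-term figure is not the chance that the tables show nothing. Simulating the 20% v 40% case and counting only excesses in Arm 1:

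- At least one term flags in about 93% of trials (about 90% in the other two cases).
- With no true difference (20% in both arms), at least one still flags in about 55%. The cause is small counts: 2 v 0 patients gives z = 0.04 / √(0.02 × 0.98 × 0.04) = 1.43, which passes.
- The composite flags an Arm 1 excess in 83%, against about 10% with no difference (half of the roughly 20% two-sided rate).

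**A pooled Grade 3 or higher row.** Suppose the table has a patient-total row and the 20% v 40% excess lies in such events. If a share b of patients have unrelated Grade 3 or higher events, independently, the total is 1 − (1 − b)(1 − c):

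- b = 10%: 28% v 46%, power about 72%.
- b = 20%: 36% v 52%, about 62%.
- b = 30%: 44% v 58%, about 55%.

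**A different set of assumptions.** Five independent organ terms, each doubling from 3% to 6%, give 1.5 v 3.0 expected patients per term and a composite of 1 − 0.97⁵ = 14.1% v 1 − 0.94⁵ = 26.6%. Normal-approximation power is 29% for one term and 61% for the composite (Fisher's exact test: 11% and 52%). With five or eight terms at 2% to 5% each, doubled or tripled, one term has 24–65% and the composite 50% to over 99%.

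**The case against.** The strongest reply is that the plan already shows more than organ-class rows. That is correct. The Grade 3 or higher, serious and discontinuation tables pool organs if they carry a total row, which Section 12.3 does not state, and the power computed above for such a row is not negligible. Injection-site reactions were Grade 1 and 2 in the phase 1 trial (Section 2.3), so they should add little there. Laboratory shift tables would show transaminase changes, though not colitis, pneumonitis or dermatitis.

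A reader might infer that the excess is likely to be missed. The documents and figures do not support that. Besides the 93% above, four or more of the six terms lean towards Arm 1 in about 77% of trials under 20% v 40%, against about 14% with no difference. A careful reader could see that pattern. But no such count is planned, and choosing one after seeing open-label results would carry little weight.

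A reader might also infer that Section 12.3 breaks a commitment in Section 5.2. It does not. The sentence on distinguishing these events stands in package-insert material that Section 5 calls background. It concerns ipilimumab-type agents, its reason is a correlation with response, and Sections 5.3 and 5.4 do not repeat it. The case rests on the comparative objective and the multi-organ toxicity.

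Finally, every event rate is assumed and the even split is unfavourable to single terms. If toxicity is concentrated in one organ, the gap shrinks. This stands. Nothing in Section 12.3 bars a grouped summary later; what would be lost is prespecification. The deferral to a statistical analysis plan under Missing Data covers efficacy imputation only.

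**Conclusion.** The point holds as a weakness of method. For a primary, comparative safety objective, the planned tables contain no summary that isolates immune-mediated toxicity across organs and no estimate of the difference between arms. They separate a spread immune signal from noise poorly: under 20% v 40% in six equal terms, scanning flags an Arm 1 excess in 93% of trials with harm and 55% without, while one composite does so in 83% and about 10%. A Grade 3 or higher total row falls between a single term and the composite in power, if it is shown and if the excess lies there.

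The sizes depend on assumed rates, on an even spread over organs, and on a level borrowed from the efficacy design. The direction is the same under the other rates tried. The conclusion is that the planned display answers the question less well than a simple alternative. It is not that harm would go unseen, or that the protocol contradicts itself.

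**What to change.** Add one prespecified table to Section 12.3, Safety Analyses: patients with at least one immune-mediated event, any grade and Grade 3 or higher, counted whatever agent the event is attributed to. Define the events by a preferred-term list fixed before database lock and drawn from those named in Sections 5.2 to 5.4 and 6.3 to 6.5. Show it by arm with the difference and its confidence interval. Any breakdown by checkpoint inhibitor should be descriptive only: 50 per arm over three drugs is about 17 each if even, and the strata are unrestricted. Keep the existing tables.

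The table should state its collection window. Section 10.6 requires all events, regardless of grade and attribution, while on study and for 30 days after the last treatment, and only related events after that. Planned treatment length differs between the ipilimumab arms (four doses alone, vaccine to month 24 in combination).

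The cost is one table and a one-off medical review of the term list, with no new data collection and no change to visits, endpoints or sample size. The downside is judgement on borderline terms, such as diarrhoea against colitis, which fixing the list before lock limits.

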## 13 Administrative and Regulatory Considerations

### 13.1 Regulatory Compliance/Good Clinical Practices

This study will be conducted in accordance with the following regulations and guidelines, to include but not limited to:

- Declaration of Helsinki (October 2000)
- Current ICH Guideline for Good Clinical Practice
- 21 CFR 50: Protection of Human Subjects
- 21 CFR 54: Financial Disclosure by Clinical Investigators
- 21 CFR 56: Institutional Review Boards
- 21 CFR 312: Investigational New Drug Application
- Dear Gene Therapy IND or Master File Sponsor Letter-3/6/2000
- Dear Gene Therapy IND Sponsor/Principal Investigator Letter 11/5/1999
- Letter to Sponsors/Researchers-Human Cells Used in Therapy Involving the Transfer of Genetic Material by Means Other Than the Union of Gamete Nuclei-7/6/2001
- Guidance for Industry: Guidance for Human Somatic Cell Therapy and Gene Therapy-3/30/1998

### ***13.2 Regulatory Documentation***

Prior to study start-up, investigators will collect the following documents, as outlined in the Essential Documents Section 8.0 of the ICH Guidelines for Good Clinical Practice:

- Signed Confidentiality Agreement
- Signed Clinical Trial Agreement, if applicable
- Up-to-date signed and dated Curriculum Vitae and copies of medical licenses for all investigators to be submitted promptly
- Financial Disclosure form for Principal and one sub/co-investigator with financial disclosure forms for all investigators to be submitted promptly
- FDA Form 1572
- IRB approval to conduct the study: IRB-approved Informed Consent Form
- Name and address of the IRB with the statement that it is organized and operates according to GCP and the applicable laws and regulations
- IRB membership roster
- Local laboratory certifications, its name and address
- Local laboratory normal ranges (a dated copy for tests to be performed during the study)
- Financial agreement, if applicable
- Signed and dated Investigator Agreement page of the final protocol and amendments, where applicable

### ***13.3 Institutional Review Board (IRB)***

This trial will be undertaken only after full approval of the protocol and addenda has been obtained from a local IRB and a copy of this approval has been received by the sponsor. The IRB must be informed of all subsequent protocol amendments issued by the sponsor. Reports on and reviews of, the trial and its progress will be submitted to the IRB by the investigator at intervals set forth in its guidelines.

### ***13.4 Informed Consent***

Each patient must give written consent and sign other locally required documents after the nature of the study has been fully explained. The informed consent form must be signed prior to performance of any study-related activity. The informed consent form that is used must be approved both by the sponsor and by the reviewing IRB. The Informed Consent should be in accordance with the Declaration of Helsinki, current International Conference on Harmonization (ICH) and Good Clinical Practices (GCP) guidelines.

### ***13.5 Administrative Requirements***

#### **Protocol modifications**

The investigator will not modify this protocol without obtaining permission from the sponsor. All protocol amendments must be issued by the sponsor, signed and dated by the investigator, and should not be implemented without prior IRB approval, except where necessary to eliminate immediate hazards to the patients or when the change(s) involves only logistical or administrative

aspects of the trial (e.g., change in monitor(s), change of telephone number(s)). In situations requiring a modification, the investigator or other physician in attendance will contact the medical monitor by fax or telephone (see Contact Information page). This contact must be made prior to implementing any departure from protocol. Contact with the sponsor must be made as soon as possible in order to outline an appropriate course of action.

### **Record Retention**

In compliance with the ICH/GCP guidelines the investigator/institution will maintain all CRFs and all source documents that support the data collected from each patient, and all trial documents as specified in Essential Documents for the Conduct of a Clinical Trial and as specified by the applicable regulatory requirement(s). The investigator/institution will take measures to prevent accidental or premature destruction of these documents. Essential documents must be retained until at least two years after the last approval of a marketing application in an ICH region or at least two years have elapsed since the formal discontinuation of clinical development of the investigational product. These documents will be retained for a longer period if required by the applicable regulatory requirements.

### **Case Report Form (CRF) Completion**

CRFs are provided for each patient. Data must be entered onto CRFs in English. All forms must be filled out in black ball-point pen. CRFs must be signed by the investigator where indicated.

All CRF corrections are to be made by the investigator or other authorized study center personnel as instructed on the CRF title page. The investigator must authorize changes to the recorded safety and efficacy data.

### **Monitoring**

NewLink Genetics (sponsor) will perform on-site monitoring visits as outlined in the Monitoring Plan for this clinical trial. The dates of the visits will be recorded by the monitor in a trial center, with the monitor visitor's log to be kept at the site. The first routine monitoring visit will usually be made within 4 weeks after enrollment has begun at that site. At these visits the monitor will verify the data entered onto the CRFs with the hospital or clinic records (source documents) and follow the procedures as outlined in NewLink Genetics SOPs. At a minimum, source documentation must be available to substantiate patient eligibility and participation, proper informed consent procedures, adherence to protocol procedures, record of safety and efficacy parameters, adequate reporting and follow-up of adverse events, administration of concomitant medication, drug receipt/dispensing/return records, study medication administration information, and date of completion and reason. Specific items required as source documents will be reviewed with the investigator prior to the study. Findings from this review of CRFs and source documents will be outlined in a Site Visit Report and discussed with the investigator. The sponsor expects that, during monitoring visits, the investigator (and as appropriate the study coordinator) will be available, the source documents will be available, and a suitable environment will be provided for review of study-related documents.

### **Data Quality Assurance**

Steps to be taken to assure the accuracy and reliability of data include the selection of qualified investigators, review of protocol procedures with the investigator and associated personnel prior to the study, and periodic monitoring visits by the sponsor. CRFs will be reviewed for accuracy and completeness by the sponsor during on-site monitoring visits and after return of CRFs to the

sponsor any discrepancies will be resolved with the investigator or designees per NewLink Genetics SOPs.

**On-Site Audits**

Representatives of the sponsor's Clinical Quality Assurance department may visit the site to carry out an audit of the study in compliance with regulatory guidelines and company policy. Such audits will require access to all study records, including source documents, for inspection and comparison with the CRFs. All efforts will be made to preserve patient privacy. Sufficient prior notice will be provided to allow the investigator proper preparation for the audit. Auditing procedures may also be conducted by any regulatory body. The investigator should immediately notify the sponsor about any audit.

**Use of Information and Publication**

All information on HyperAcute cancer immunotherapy, NewLink operations, patent application, manufacturing process, basic scientific data supplied by the sponsor to the investigator and not previously published is considered confidential and remains the sole property of NewLink Genetics. The investigator agrees to use this information only to accomplish this study and will not use it for other purposes without the sponsor's written consent.

The investigator understands that the information developed in the clinical study will be used by NewLink in connection with the continued development of HyperAcute immunotherapy and thus may be disclosed as required to other clinical investigators or government regulatory agencies. To permit the information derived from the clinical studies to be used, the investigator is obligated to provide the sponsor with all data obtained in the study.

Any publication or other public presentation of results from this study requires prior review of NewLink Genetics. Draft abstracts, manuscripts and materials for presentation at scientific meetings should be provided to the sponsor at least 30 working days prior to abstract or other relevant submission deadlines or as outlined in the clinical trial agreement.

